4.5.1.16 CDR Progression

When a change from the prior visit's global CDR score is recorded, a review of that participant's CDR scoring sheets from that visit will automatically be triggered and performed by the CRO responsible for quality assurance of cognitive assessments in order to confirm that the total CDR score was derived correctly.

4.5.1.17 Medical History

A complete medical history should include a negative or positive history for risk factors for pneumonia, including asthma, chronic obstructive pulmonary disease (COPD), heart disease, and smoking; and any other potential risk factor considered significant in the investigator's judgment.

4.5.2 Screening and Pretreatment Assessments

Participants must sign an Informed Consent Form before any screening evaluations or measurements are performed. Participants must satisfy all of the inclusion criteria and none of the exclusion criteria prior to randomization. Information regarding consented participants, who are not subsequently randomized, will be kept in a screening log.

All screening evaluations must be completed within 56 days and reviewed to confirm that participants meet all eligibility criteria before the first injection of study drug.

Informed consent for participation in the study must be obtained before performing any study-specific screening tests or evaluations. Informed Consent Forms for participants who are not subsequently enrolled will be maintained at the study site. In addition, the randomization in IxRS will not occur until the participant's eligibility has been confirmed by the Medical Monitor or designated staff.

Participants who are found to be ineligible for entry into the study, on the basis of inclusion/exclusion criteria, will not be re-screened with the following exceptions:

- Participants who fail to meet criteria based on TSH levels may be re-screened once after initiation of treatment for the underlying disease and maintenance of treatment at a stable dose for ≥ 1 month prior to Day 1
- Participants who fail to meet criteria based on vitamin B12 levels may be re-screened once after initiation of treatment for the underlying disease and maintenance of treatment at a stable dose for ≥ 1 month prior to Day 1
- Participants who test positive for drugs of abuse (except cannabinoids) in their urine at screening may be re-screened one additional time
- Participants who are ineligible because of need for medical treatment of infection or need for medical treatment of minor, non-excluded medical condition(s) diagnosed during screening, or who have minor but clinically significant blood or urine laboratory abnormalities requiring intervention (for example, stopping a medication), may be re-screened once, after the condition(s) have stabilized and

after doses of treatment medications for these condition(s) have been discontinued for at least 30 days, or have been stabilized for at least 30 days

- Participants who are ineligible because of cognitive screening results may be re-screened once, but not earlier than 3 months after the first assessment. Screening evaluations must be repeated in these participants. Screening, pretreatment tests, and evaluations will be performed within 56 days prior to Day 1 of Week 1, unless otherwise specified.
- Participants who previously withdrew consent for study participation during the screening period, but are otherwise eligible, may be re-screened once but not earlier than 3 months after the first assessment. Screening evaluations must be repeated in these participants. Screening, pretreatment tests, and evaluations will be performed within 56 days prior to Day 1 of Week 1, unless otherwise specified.

A participant may be re-screened once, for any of the exceptions just described, at which time the exception must be addressed. Upon screening, if a different exception arises, 1 additional re screening is possible, at which time all exceptions must be addressed; however, a participant may be re-screened a total of 2 times, at most, for the exceptions listed above.

In addition to this re-screen limit, participants who are ineligible because of unavailability of a study partner may be re-screened multiple times to attempt to find an available study partner but not earlier than 1 month after the first assessment of the most recent screening period. Screening, pretreatment tests, and evaluations will be performed within 56 days prior to Day 1 of Week 1, unless otherwise specified.

Laboratory testing, cognitive/functional assessments or imaging assessments that are repeated for administrative or technical issues (e.g., breakage of a sample vial, not evaluable images) are not considered to constitute “re-screening.” In these cases, the screening window may be extended if approved by the Medical Monitor.

Please see the study flowchart provided in [Appendix 1](#) for the screening and pretreatment assessments.

4.5.3 Assessments During Treatment

All assessments will be performed on the day of the specified visit unless a time window is specified. Assessments scheduled on the day of study drug administration should be performed prior to study drug injection or infusion, unless otherwise noted. For SC administration, please see the study flowcharts provided in [Appendix 1](#) and [Appendix 2](#) for the schedule of treatment assessments. For participants who decide to switch to IV dosing, the study flowcharts provided in [Appendix 3](#) and [Appendix 4](#) should be followed, starting from the visit when the first IV dose is administered.

4.5.4 Remote Assessments

In the case of coronavirus disease 2019 (COVID-19) or similar events where in-person assessments are not possible, remote assessments may be allowed ([Appendix 1](#) and [Appendix 2](#)). Any assessments that could not be collected remotely should be collected in-person as soon as feasible, even if out of the protocol-defined assessment window, particularly those related to the primary outcome or safety assessments.

4.5.5 Study Completion

The common-close study design requires that all participants should remain on their randomized treatment allocation until the last participant completes their Week 260 visit (subject to practical considerations regarding scheduling of final study visits that are outlined below). An end of treatment or ET visit (ET-A or ET-B), including all assessments scheduled per study flowchart should be completed at the end of the blinded treatment period, 4 weeks after the final dose. Following the completion of the randomized, placebo-controlled, double-blinded treatment period in Study Period A, participants will be offered the opportunity to continue to receive study drug until the results of the study are known and post-trial access to crenezumab is started (via an OLE or other program) or development of crenezumab is discontinued. For participants who do not choose to continue study drug in Study Period B, a final safety follow-up visit will be completed 16 weeks after the final dose.

In order to minimize site burden and to facilitate scheduling, sites will be notified at least 4 months prior to the date of the common close and as such will be able to utilize upcoming planned visits to schedule the study completion assessments.

Participants who enrolled early in the study and have been in the study longer should have their study completion visits scheduled earlier where possible. The Sponsor will provide guidance to sites to facilitate scheduling when they are notified that the end of study is approaching.

Please see the study flowchart provided in [Appendix 2](#) or [Appendix 4](#) for assessments to be performed at the study completion visit (ET-A or ET-B) and the safety follow-up visit.

4.5.6 Early Termination Visit

Participants who discontinue from blinded treatment prior to completion of Study Period A (early treatment discontinuation) will be asked to stay in the study for continued safety and efficacy assessments at selected evaluation visits following completion of an ET visit (see study flowchart in [Appendix 1](#), [Appendix 2](#), [Appendix 3](#), and [Appendix 4](#)). Participants who discontinue from the study (ET), or who discontinue from blinded treatment and elect to no longer remain in the study, will be asked to return to the clinic for an ET visit (see the study flowchart in [Appendix 2](#) for participants receiving SC study drug and [Appendix 4](#) for participants receiving IV study drug). The ET visit should be 4 weeks from last dose. In addition, a final safety follow-up visit

should be completed 16 weeks after last dose to ensure adequate washout of study drug but may be scheduled sooner if needed.

Please see the study flowchart provided in [Appendix 2](#) or [Appendix 4](#) for assessments to be performed at the study completion/ET visit.

Participants that are study drug non-compliant may be withdrawn from study treatment. As standard guidance, this refers to the following: Participant misses more than 2 doses within a single, 6-month period; a one-time exception of 3 missed doses within a 6-month period will be allowed. In rare circumstances (e.g., hospitalization), the Medical Monitor has the discretion to allow additional missed doses.

In order to maximize the opportunity for all active trial participants to receive the higher dose (60 mg/kg IV) of study drug, participants who have withdrawn from study treatment *in Study Period A*, but remain in the study for safety and efficacy assessments will be permitted a one-time opportunity to return to the study and to receive the higher IV dose, provided they did not discontinue treatment due to an adverse event related to study drug, the investigator judges it is safe to restart study drug, and the participant consents to receive IV administration of study drug going forward. If the participant has not completed a complex visit within 6 months of restarting study drug, a complex visit should be completed prior to reinitiating study drug. The investigator may also order unscheduled laboratory assessments as necessary to ensure safety and appropriateness to resume study drug.

If a participant discontinues from the study (ET) or discontinues from study drug treatment and elects to no longer stay in the study, ET Visit A should be completed if the last visit occurred more than 12 weeks after functional, behavioral and cognitive assessments were performed; ET Visit B should be performed if the last visit occurred within 12 weeks of functional, behavioral and cognitive assessments. The final safety follow-up visit should be scheduled 16 weeks from last dose.

Study Period B: If a participant enters Study Period B, but wishes to stop study treatment before the end of Study Period B, a safety follow-up visit should be completed 16 weeks from the last dose.

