4.4.1.3 Prohibited Therapies

The following are prohibited therapies:

- Typical anti-psychotic medications
- Barbiturates
- Anti-seizure medication for seizure indication
 - Non-sedating anti-seizure drugs (e.g., pregabalin) use for non-seizure indication are permitted with Medical Monitor approval.
- Anti-Parkinsonian medications
- Prescription stimulant medications (e.g. methylphenidate, dextroamphetamine, etc.)
 - Over-the-counter stimulants, such as caffeine, nicotine, and those found in cold and flu preparations (e.g., pseudoephedrine), are allowed.
- Long term use of anticoagulants
- Cholinesterase inhibitors and/or memantine, with the following exception:
 - Participants enrolled in the study who develop AD dementia will be permitted to take approved AD treatments (cholinesterase inhibitors and/or memantine).

During the study, participants will be permitted to receive any treatment deemed necessary by the investigator for the management of their disease.

However, participants requiring commencement of excluded therapies may not be able to receive further doses of study drug if initiation of the excluded medication increases the risk of receiving study drug (such as anticoagulants). Participants who are withdrawn from study drug *during Study Period A* will be invited to continue to be followed at the evaluation visits for safety, clinical and biomarker assessments, selected PK, exploratory PD, and ADA status, as specified in the study flowchart (see [Appendix 1](#), [Appendix 2](#), [Appendix 3](#), and [Appendix 4](#)).

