4.5.8 Study Period B Visits and Assessments

All assessments will be performed on the day of the specified visit unless a time window is specified. Assessments scheduled on the day of study drug administration should be performed prior to study drug injection or infusion, unless otherwise noted.

Study conduct and procedures during Study Period B are the same as for Study Period A (see Section [4.5.1](#)), though the frequency may be different. For SC administration, please see the study flowcharts provided in [Appendix 5](#). For IV administration, please see the study flowchart provided in [Appendix 6](#). If participants terminate participation in Study Period B, or Study Period B is terminated by the Sponsor due to discontinuation of the development of crenezumab, or participants complete Study Period B and do not enter an OLE or otherwise continue on crenezumab, participants will be asked to complete a final safety follow-up visit 16 weeks after their last dose of study drug ([Appendix 5](#) and [Appendix 6](#)).

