Single 12-Lead ECG ⁱ				x		x	x	x
Physical and neurologic examinations ^j				x		x		x
Serum chemistry and hematology ^{k,l}				x		x		x
MRI ^m						x		
Optional CSF ^{n,p}						x		
Optional Tau-PET ^{o,p}						x		
Amyloid-PET ^p						x		
Evaluate criteria for MCI/AD			x	x	x	x	x	
GDS ^{q,r}			x	x	x	x	x	

Appendix 5
Study Flow Chart for Study Period B: SC Dosing (cont.)

	W1 and Every 2 Weeks Thereafter ^a	W13	W25	W53	W77	W105	W157 and Every 52 Weeks Thereafter	ET/SFU Last Dose + 16 W ^b
Assessment window	(±7d)	(±7d)	(±7d)	(±7d)	(±7d)	(±7d)	(±7d)	(±7d)
SMC ^{q,r}			x	x	x	x	x	
API ADAD Cognitive Composite Battery ^s			x	x	x	x	x	
FCSRT ^s			x	x	x	x	x	
Trail Making Tests A and B ^s			x	x	x	x	x	
RBANS ^s			x	x	x	x	x	
SPCQ ^{u,r,t}			x	x	x	x	x	
CDR ^{q,r,t}			x	x	x	x	x	
FAST ^{r,t}			x	x	x	x	x	
NPI ^{r,t}			x	x	x	x	x	
Suicidality assessment ^{q,r}			x	x	x	x	x	
Study drug administration ^{v,w,x}	x	x	x	x	x	x	x	
Concomitant medication review ^r	x	x	x	x	x	x	x	x
Adverse event review ^r	x	x	x	x	x	x	x	x

AD = Alzheimer's disease; ADA = anti-drug antibody; ADAD = autosomal-dominant Alzheimer's disease; CDR = Clinical Dementia Rating; CERAD = Consortium to Establish a Registry for Alzheimer's Disease; CSF = cerebrospinal fluid; d = day; ET = early termination; FAST = Functional Assessment Staging of Alzheimer's Disease; FCSRT = Free and Cued Selective Reminding Test; GDS = Geriatric Depression Scale; MCI = mild cognitive impairment; MMSE = Mini-Mental State Examination; MRI = magnetic resonance imaging; NPI = Neuropsychiatric Inventory; PD = pharmacodynamic; PET = positron emission tomography; PK = pharmacokinetic; RBANS = Repeatable Battery for the Assessment of Neuropsychological Status; SFU = safety follow-up; SMC = Subjective Memory Checklist; SPCQ = Study Partner Characterization Questionnaire; W = week.

Appendix 5
Study Flow Chart for Study Period B: SC Dosing (cont.)

- ^a Week 1 is the first dose in Study Period B and may occur on the same day as the final ET-A or ET-B visit in Study Period A after all ET assessments are completed and the investigator deems dosing is appropriate.
- ^b Early termination visit/SFU visit, occurring when someone terminates prior to the end of the Study Period B, should be done 16 weeks after the last dose of study drug. Participants who continue crenezumab treatment after the end of Study Period B will not have a “last dose + 16 weeks visit”.

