- ^p Cerebrospinal fluid and/or PET assessments to be performed at Week 105 or ET if ET is prior to Week 105. Cerebrospinal fluid and/or PET assessments will not be performed at the ET visit if less than 6 months have elapsed since the previous CSF and/or PET assessment. If needed because of operational constraints, CSF and/or PET assessments can be performed up to 3 months after Week 105. Cerebrospinal fluid and PET assessments should not be done on the same day, but at least 24 hours apart. Amyloid PET and Tau PET assessments should not be done on the same day, but at least 24 hours apart.
- ^q Cognitive and selected other assessments (GDS, SMC, CDR, and suicidality assessment) should not be administered to the participant immediately after dosing or any potentially stressful procedures (e.g., blood draws, CSF sampling, imaging). Also, participants should not perform these assessments while fasting. For each participant, best efforts should be exerted to perform subsequent assessments at the same time of day as the baseline assessments.
- ^r In exceptional instances, these assessments are permitted by phone or video technology.
- ^s The API ADAD Composite Cognitive Test Battery includes the following assessments which should be administered in this order: MMSE, Multilingual Naming Test, Word List: Memory, CERAD Constructional Praxis, Word List: Recall, Word List: Recognition, Raven's Progressive Matrices—Set A. The API ADAD composite should also be administered before administering FCSRT, Trail Making Test, and RBANS.
- ^t The SPCQ, CDR (study partner portion), FAST, SMC, and NPI should be administered to the same study partner throughout the study. Best efforts should be exerted in order for the study partner to be present for all visits requiring study partner assessments. In rare instances, for which the study partner cannot be present in person, these assessments may be administered by telephone.
- ^u Completed prior to the administration of all other study partner assessments at each visit.
- ^v Study drug administration should be performed only after all assessments/rating scales have been completed (unless indicated otherwise). Study drug will be administered to participants by injection (full details in the pharmacy manual). Participants must be observed for a minimum of 15 minutes after dosing.

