5.10.1 Efficacy Analyses

All efficacy analyses will include data from Study Period A, Study Period B, and the OLE study; the analysis population will be based on mITT. *The delayed start efficacy analyses will be triggered 2 years after the last efficacy visit in Study Period A.*

Two types of efficacy analyses are prespecified depending on the endpoint type: delayed-start analyses for continuous endpoints and rank-preserving structural failure time (RPSFT) analyses for time-to-event endpoints.

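### Participants who stop study drug early in Period B have no scheduled cognitive, CDR or MCI/AD assessment afterwards, although SAP 5.10 analyses exactly these endpoints

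*Protocol*

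**What the plan says.** **Period A.** Under Protocol 4.5.6, a participant who stops blinded treatment early "will be asked to stay in the study for continued safety and efficacy assessments at selected evaluation visits". Section 4.4.1.3 says that those withdrawn from drug during Period A "will be invited to continue to be followed at the evaluation visits for safety, clinical and biomarker assessments". Those who leave the study have an ET visit 4 weeks after the last dose. It takes the ET-A form, with cognitive battery, CDR and MCI/AD evaluation, if these were last done more than 12 weeks before.

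**Period B.** The rule in 4.5.6 for someone who enters Period B is: "wishes to stop study treatment before the end of Study Period B, a safety follow-up visit should be completed 16 weeks from the last dose". Section 4.5.8 adds that, when participation ends without continued crenezumab, "participants will be asked to complete a final safety follow-up visit 16 weeks after their last dose of study drug". Footnote b of Appendices 5 and 6 makes this a single combined ET/SFU visit that "should be done 16 weeks after the last dose of study drug".

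**Flowcharts.** In both appendices the MCI/AD evaluation, API composite, FCSRT, RBANS and CDR are marked at W25, W53, W77, W105 and yearly from W157. The ET/SFU cell is empty for each. Imaging and CSF are treated differently: "Cerebrospinal fluid and/or PET assessments to be performed at Week 105 or ET if ET is prior to Week 105" (footnote p), and footnote m does the same for MRI.

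**Analyses.** SAP 5.10.1: "All efficacy analyses will include data from Study Period A, Study Period B, and the OLE study". Section 5.10.1.1 formally tests the composite and the FCSRT Cueing Index. Section 5.10.1.2 applies RPSFT to time to non-zero CDR and time to MCI or dementia.

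**The concern.** The endpoints analysed in Period B are the ones not collected when a participant stops early. Three features make the loss more than cosmetic.

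- **Time-to-event endpoints.** Protocol 5.3.1.7 treats expected AD progression as efficacy data, not as an adverse event. The adverse event review at the safety visit is therefore not meant to pick up expected progression since the last scheduled evaluation.
- **Delayed-start model.** In SAP Appendix 3, T_i is the first assessment after entry to Period B, and the post-switch term applies only at later times. Under the flowcharts T_i is W25. A Period A placebo carrier whose last cognitive visit is W25 contributes no observation to the post-switch slope.
- **No sensitivity analysis.** The Period A primary analysis has discontinuation and control-based sensitivity analyses. SAP 5.10 and Appendix 3 specify none for the Period B analyses, which rest on missing-at-random and non-informative censoring.

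If leaving is related to decline, the missing outcomes would be the informative ones.

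**Working it through.** **Plan's own figures.** The documents give no Period B sample size, power or dropout rate to reproduce. The Period A power statement does reproduce. With 100 × (1 − 0.25) = 75 per arm, 30% reduction, CV 65% and two-sided 0.05: (0.30/0.65) × √(75/2) = 2.83, and Φ(2.83 − 1.96) = 80.7% (80.2% by t-test). It says nothing about Period B.

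**Time unobserved per stopper.** Inputs are the visits W25, W53, W77 and W105 (Appendices 5 and 6), with the last Period A score taken as Week 1. Assumption: stop times are uniform over W1 to W105 (104 weeks).

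- Gaps: 24, 28, 24, 28 weeks.
- Mean time on drug since the last assessment = Σgap²/(2 × 104) = (576 + 784 + 576 + 784)/208 = 2720/208 = 13.1 weeks (maximum 24 to 28).
- To the safety visit: 13.1 + 16 = 29.1 weeks.
- After W105 the gap is 52 weeks, so the mean there would be 52/2 = 26 weeks on drug.

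**Assessments lost per stopper.** A stopper misses every scheduled visit after the stop: (24 + 52 + 76 + 104)/104 = 256/104 = 2.46 of 4, or 61.5%.

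**Share lost overall.** Period B dropout is an assumption, so a range is shown (dropout × 0.615):

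| Dropout over the period | Scheduled assessments lost |
|---|---|
| 5% | 3.1% |
| 10% | 6.2% |
| 25% | 15.4% |

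**What bias could look like.** A simulation of a delayed-start model of the Appendix 3 form used 84 carriers per arm (the number in SAP Appendix 2), a 30% slope benefit and a true post-switch slope change of 0.30 per year. Dropout was made to depend on the Period B slope by assumption. There were 150 replicates per scenario, and the slope break was placed at Period B entry. Shifts are relative to complete follow-up:

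| Scenario (dropout, former placebo / crenezumab) | Slope change: complete → scheduled visits only → plus a score at stopping | Δ2: complete → scheduled visits only |
|---|---|---|
| 9% / 10% | 0.295 → 0.328 → 0.321 | 1.702 → 1.683 |
| 9% / 5% | 0.309 → 0.344 → 0.336 | 1.744 → 1.686 |
| 25% / 24% | 0.314 → 0.398 → 0.378 | 1.780 → 1.703 |
| 24% / 19% | 0.307 → 0.391 → 0.370 | 1.817 → 1.679 |

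The slope change shifts by +0.03 to +0.08 per year (about 11% to 28% of 0.30), and the end-of-period benefit Δ2 by −0.02 to −0.14 (1% to 8%). One score at stopping removes about a fifth to a quarter of the slope-change shift. These figures follow from the assumed dropout mechanism and variance components. They show direction and scale and are not estimates for this trial. The simulation does not cover the RPSFT endpoints.

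**The case against.** The strongest points on the other side, and what stands of each:

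- **Participants are not abandoned.** Correct. A 16-week safety visit is required, Section 4.6 asks for every effort to obtain information on early leavers, and ARIA stoppers are kept (3.5.2.2) or invited to stay (4.3.1.3). Section 4.5.8 also says procedures match Period A, but it points to the assessment definitions in 4.5.1. None of this puts the battery at the ET/SFU visit or covers other stoppers. The ARIA sections and 4.5.6 should be reconciled.
- **The comparison with Period A is not like for like.** Also correct. Period A collects the battery at a 4-week ET visit, and its 16-week safety visit has none. Period B has no 4-week visit.
- **The imaging contrast has an innocent explanation.** Largely so. MRI, PET and CSF are each scheduled once in the first two years of Period B, at W105, so an early leaver would otherwise have none. Cognition has four visits by then.
- **Decline-related exit is not shown.** This stands. Progression is not among the listed withdrawal reasons, and participants who develop dementia may take approved AD drugs and remain. The mixed model also retains all Period A scores and those Period B scores obtained before exit.
- **The model has no off-drug term.** A score 16 weeks after the last dose would sit on the crenezumab slope. This is largely met: Protocol 4.10.4.1 regards those 16 weeks as treatment-exposed, and SAP 5.3.2 uses all observed Period A values after withdrawal for an adverse event or pregnancy. It remains a choice that SAP 5.10 should state.

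**Conclusion.** The gap is real on the text. An early stopper in Period B has no scheduled cognitive, CDR or MCI/AD assessment after stopping, unless the ARIA provisions apply. The delayed-start and RPSFT analyses lose the last score and any later progression. On average about 13 weeks on drug go unobserved, or about 29 weeks to the safety visit, assuming uniform stop times over W1 to W105.

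A reader might infer more, and the documents do not support it:

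- **That stoppers are not followed at all.** The gap concerns clinical efficacy only.
- **That the Period B results are biased by decline-related dropout.** No Period B dropout rates or reasons are given, so this is plausible but unquantified.
- **That the trial's main conclusion is at risk.** The Period A primary analysis does not use these data, and Period B analyses are exploratory if the study is terminated on Period A results.

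This is a worthwhile, inexpensive improvement, not a flaw that undermines the trial.

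**What to change.** 1. **Flowcharts.** Add the API composite, FCSRT, CDR and MCI/AD evaluation to the ET/SFU column of Appendices 5 and 6 for all early leavers. Protocol 4.5.1.15 bases the MCI/AD judgement also on RBANS, SMC and FAST, and on NPI for dementia, so these and the study partner are needed too. The Period A 12-week condition need not be carried over: at a visit 16 weeks after the last dose, it is met for any battery done on or before the last dosing day.
2. **Apply it regardless of genotype.** Restricting the assessment, or any invitation, to carriers would reveal mutation status to blinded participants and site staff.
3. **SAP 5.10.** State that these scores and events enter the delayed-start and RPSFT analyses under treatment-policy handling, as Period A does after withdrawal for an adverse event or pregnancy.
4. **Optional.** Invite all blinded participants who stop drug, not carriers only, to the remaining cognitive visits. In the illustration, a single score at stopping recovers only part of the loss.

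**Cost.** A flowchart and wording change, plus one test session by existing raters at a visit already scheduled, for early leavers only. The downsides are added burden for participant and study partner, and scores taken up to 16 weeks after the last dose. Item 4 adds further voluntary visits.
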